Title: Exploring the effects of an intravaginal lactic acid gel on the vaginal microbiome

Version Date: November 23, 2022

Principal Investigator: [name] MPH

Co-Investigator(s): [name], DO, [name] MPH

Research associates: [name], [name] and [name] (SRI)

Research Site(s): The Queen's Medical Center, [name]

Abbreviations:

- **BV: bacterial vaginosis**
- **CV: candida vaginitis**
- **HRT: hormone replacement therapy**
- **CST: community state types**

Section I: Purpose and Background

1. Specific aims and objectives:

This project aims to investigate if the contraceptive method, Phexxi, causes changes to the composition of the vaginal microbiome. We hypothesize that regular use of Phexxi will cause increased colonization of lactic acid-producing lactobacilli, which could have positive effects in the way of preventing recurrent episodes of BV and candida infections.

Primary outcomes

- To assess if the use of Phexxi causes changes in the vaginal microbiome
- To assess if the use of Phexxi decreases vulvovaginitis symptoms in study participants

Secondary outcome

- To assess patient satisfaction/acceptability of this intervention as a therapeutic/prophylactic agent for recurrent vulvovaginitis

2. Background, significance, and rationale

Bacterial vaginosis (BV) and candida vaginitis (vaginal yeast infection) are debilitating, long-term conditions which have been associated with decreased confidence and self-esteem, difficulty with sexual intimacy, and decreased quality of life amongst women who suffer from one or both chronically. BV has a particularly high rate of recurrence, with an estimated 30% of infections recurring within three months of treatment, and an estimated 50% of infections recurring within six months of initial treatment¹.

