The existing research on lactic acid-containing gel is promising. Of all studied methods of vaginal delivery of lactic-acid, including a douching system, a slow-release delivery pessary, lactic acid capsules, and a lactic acid-containing gel, the lactic acid-containing gel seems to be most effective. One study shows that the use of lactic acid gel as a treatment for bacterial vaginosis is comparable, but not superior to, the use of metronidazole^{8,9,10}. Currently, no research has been done on lactic acid gel as a prophylactic agent for patients who suffer from recurrent BV and/or yeast infections. This study aims to explore the feasibility and efficacy of a lactic acid-containing gel as prophylaxis against recurrent BV/yeast infections.

While several studies have been done which suggest that, as a treatment, intravaginal lactic acid gel is non-inferior to metronidazole, there have been no studies which explore its potential as a preventative agent. Compared to antibiotic therapies, lactic acid supplementation may be a more cost effective way to prevent BV and/or yeast infections, thereby reducing morbidities related to these conditions in patients who suffer from recurrent infections.

Section II: Criteria for Subject Selection

1. Number of subjects:

We will enroll a total of 22 patients. Using the Viechtbauer et al. method for calculating sample size in pilot studies¹¹, with a confidence level of 95% and probability of error prevalence estimated to at least 15%, the recommended sample size is 20. To account for exclusions and drop outs (estimated to be 10%), we should enroll a total of 22 patients.

2. Demographics of subjects:

Patients who undergo screening and are found to meet inclusion criteria will be invited to participate in this study.

Inclusion criteria

- Age 18-54
- Female
- Pre-menopausal
- Can speak and read in English
- Displays capacity for informed consent
- Has had 2 or more documented and/or self-reported episodes of symptomatic BV or candida infection in the last year, requiring, over-the-counter or prescription treatment

Exclusion criteria

- Pregnant or trying to become pregnant
- Post-menopausal
- Using NuvaRing device
- A past medical history of kidney disease, recurrent UTI, and/or urinary tract abnormalities
- Current UTI
- Using Phexxi as a contraceptive during the collection period of the study

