*Note: NuvaRing is the only medication that will be included in the exclusion criteria. While we will ask all participants to provide a list of medical conditions they have and a list of medications they are currently taking, these will be for the purposes of data analysis, and to account for possible confounders of our data.

*Note: patients do not have to be symptom-free to participate in this study. However, as stated below, if they receive antibiotic/antifungal treatment prior to starting the study, we will ask them to wait 10 days after the completion of the treatment before they collect their first swab, in order to allow for the restoration of their baseline bacterial flora.

3. Vulnerable subjects:

N/A. Pregnancy is listed as an exclusion criteria, and no minors or incarcerated persons will be included in this study.

Section III: Methods and Procedures

1. Study design and methods

This is a single center, prospective trial, which comprises of a pre-post study design will be looking at the vaginal microbiome makeup of participants before and after a four-week course of Phexxi. The primary outcomes will be an increase in lactic acid-forming lactobacilli, as well as a decrease in patient-reported symptoms of vulvovaginitis.

This study will be based at the Queen's Medical Center (QMC), [name]. Eligible patients will be approached by participating clinicians (all doctors providing care at the 1004 clinic, as delineated in the LOA form) to assess interest in study participation.. The principal investigator will review the weekly schedule for the 1004 clinic and alert the attending physicians of patients who may be eligible for the study based on chart review. A HIPAA waiver will be required for this stage of recruitment, as the principal investigator would otherwise not be accessing these patient's charts. The attending physician staffing the 1004 clinic will ask the flagged patients if they are interested in learning about the study and review general study objectives with patients. If the patient is interested in participating, the research associates will approach the patient to more thoroughly screen, then conduct the informed consent process. Informed consent will be collected from every participant prior to the start of the study.

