The intervention will take place on a rolling basis, as patient participation will have no bearing on other participants. The intervention itself will take place over thirty days. 8 pre-filled vaginal inserters with vaginal gel, will be provided to each of the participants with verbal and written instructions for application. Patients will be instructed to use Phexxi twice per week, on the same days every week. Throughout the 30 days, participants will also be asked to keep a diary of events (Appendix E) occurring when they used the product, such as intercourse or menses, as well as record any symptoms or side effects they noticed when using the product. The diary can be sent back with the second specimen vial. Disposal of the product may be done in a regular waste basket.

Approximately 30 days after completion of the intervention, participants will receive an email reminder to collect and send a third collection swab in (Appendix G) for analysis. This email will also include the link for the third and final set of surveys (B and C).

2. Data analysis and monitoring (include adverse event reporting procedures)

The pre-and post-intervention results will be compared with the subjects to serve as their own controls in this pilot study. To assess for the primary outcomes, each bacteria identified in the NextGen analyses of the composition of the pre-intervention microbiome sampling will be individually named, then classified as either “lactic acid-forming (LAF)” or “not lactic acid-forming (NLF)”. This will allow us to identify which CST each participant falls under prior to the study, and to assess if they can be classified under a different CST at the end of the study. It also allows us to conduct an independent t-test to test for significance between two variables (LAF/NLF) pre and post-intervention.

Demographic data will be collected from patient surveys. Demographic information to be collected will include age, ethnicity, number of reported vaginal yeast infections or BV infections in the last year, type of contraception used, type of diet, and medical comorbidities/current medications. This demographic information will allow us to perform a multiple regression analysis on our data set to account for confounding factors in our study population.

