Patients of the 1004 clinic who have been seen two or more times in the past year for recurring symptoms of vulvovaginitis will be screened for this study. In addition, informational posters will be put up in clinic offices in order to invite patients who are interested in the study to undergo screening for suitability of participation.

2. Process of consent:

Each week, the principal investigator will review the records of patients scheduled for appointments in the 1004 clinic for eligibility. These patients will be informed about the study during their visit, and if interested, a research team member will perform a thorough analysis for eligibility. Researcher or research associate will approach patients who are screened as eligible to enroll in the study. A standard, IRB-approved consent form will be used. The consent form will be reviewed, explaining the nature and purpose of the study, intervention and tasks associated with participating, as well as all risks and benefits associated with participation. Research associates can answer questions about the study and complete informed consent. If questions are outside of research associates' scope, then physicians will be available to answer these questions. If enrolled, patients will be provided a signed copy of the consent form.

3. Subject capacity assessment procedures: Not applicable

4. Subject/Representative comprehension:

Patient must be able to understand and communicate effectively in English. As part of obtaining informed consent, patients must be able to demonstrate comprehension of the risks and benefits of study to the researcher. If they are unable to do so using basic English, they will not be deemed appropriate for participation in this study.

5. Debriefing procedures for non-disclosed information (if applicable): not applicable
6. Documentation of consent/assent:

An IRB-approved consent form will be used to document consent. Subjects will be provided with a copy of the consent form. A copy of the signed consent form will be scanned into the subject's medical record.

7. Costs to the subject: No monetary cost will be incurred by the subject, unless the patient develops side effects to the study drug and needs to seek medical attention for these side effects. As stated above, if this occurs, the patient will be responsible for using their insurance plan to cover the costs incurred.

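### The primary aims and hypothesis are worded as effects of Phexxi, but an uncontrolled single-group pre-post study can only describe change over time

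*Protocol*

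**What the plan says.** Section I.1 of the Protocol gives two primary aims: "To assess if the use of Phexxi causes changes in the vaginal microbiome" and "To assess if the use of Phexxi decreases vulvovaginitis symptoms in study participants". The hypothesis in the same section says that regular use will bring about more colonisation by lactic acid-producing lactobacilli. Section I.3 adds that the study explores efficacy as prophylaxis.

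On design, Section III.1 states: "This is a single center, prospective trial, which comprises of a pre-post study design". Section III.2 states: "The pre-and post-intervention results will be compared with the subjects to serve as their own controls in this pilot study". No concurrent control, randomisation or second pre-treatment measurement is described. Section III.2 also plans a multiple regression on survey data (age, ethnicity, infections in the last year, contraception, diet, comorbidities and medications) to deal with confounding.

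On who enters, Section II.2 requires: "Has had 2 or more documented and/or self-reported episodes of symptomatic BV or candida infection in the last year". A note in that section adds: "patients do not have to be symptom-free to participate in this study". Section V.1 describes the screening: "Patients of the 1004 clinic who have been seen two or more times in the past year for recurring symptoms of vulvovaginitis will be screened". Posters in clinic offices are a second route.

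On timing, Section III.1 has all swabs collected at home. The baseline swab is taken at least 10 days after menses and, for women on an acute antibiotic or antifungal course, 10 days after it ends. Collections 2 and 3 follow at the end of the 30-day intervention and 30 days later. The symptom items (Appendix C) refer to the past week.

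**The concern.** The aims ask what the gel does. The design shows only what happens to treated women over about two months. Every woman receives the gel and every post-baseline measurement comes after she has started it, so exposure and elapsed time coincide completely. Whatever else moves symptoms or flora over that period is counted in the same change.

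This matters more than usual here because the condition fluctuates and recurs, entry depends on a recent history of episodes, symptoms at entry are allowed, and a one-week recall score follows short-term swings. A significant pre-post change would answer the aims as written, although it could also arise with an inert product. A null or adverse change could equally hide a benefit if relapse after recent treatment offsets it.

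**Working it through.** **The plan's own figure.** Section II.1 gives 20 evaluable and 22 enrolled. The pilot formula gives n = ln(1 − 0.95)/ln(1 − 0.15) = 18.4, so 19 against the stated 20. For dropout, 20 × 1.10 = 22, or 20/0.90 = 22.2, so 23. The stated figures are reproduced to within one patient. They do not bear on this point except that n = 20 is used below.

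**What the data can identify.** Write each woman's change as τ + δ + β′x + error, where τ is the gel effect, δ is everything else that happens over time, and x holds her survey characteristics. With no untreated woman and no second pre-treatment measurement, only τ + δ can be estimated. The regression can show which women change more. It cannot split τ from δ, however many terms are added.

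**Illustration for the symptom score, gel effect zero.** The documents give no correlation or baseline elevation, so these are assumptions: baseline lies z = 0.5 to 1 SD above the population mean, and test-retest correlation is r = 0.5 to 0.7. Then the expected fall is (1 − r)z, the SD of change is √(2(1 − r)), and d is their ratio. The chance of p < 0.05 comes from the noncentral t with 19 degrees of freedom and noncentrality d√20 (two-sided paired test).

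| z | r | Fall (SD) | SD of change | d | Chance of p < 0.05 |
|---|---|---|---|---|---|
| 0.5 | 0.5 | 0.25 | 1.00 | 0.25 | 19% |
| 0.5 | 0.7 | 0.15 | 0.77 | 0.19 | 13% |
| 1.0 | 0.5 | 0.50 | 1.00 | 0.50 | 56% |
| 1.0 | 0.7 | 0.30 | 0.77 | 0.39 | 38% |

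The nominal rate is 5%. The formula (1 − r)z applies to elevation above the population mean, not above a woman's own usual level.

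**Sensitivity to how close baseline is to selection.** Suppose women enter when a selection score exceeds a cut-off that a share q of 0.5 or 0.3 exceeds. The mean selection score is then λ = φ(c)/q = 0.80 or 1.16, and the expected change is (corr(selection, follow-up) − corr(selection, baseline)) × λ. All correlations are assumed.

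| Corr. of selection with baseline | Corr. of selection with follow-up | Spurious fall (SD) | Chance of p < 0.05, n = 20 |
|---|---|---|---|
| 1 (baseline is the selecting measurement) | 0.3 to 0.7 | 0.24 to 0.81 | 28% to 92% |
| 0.6 to 0.8 | 0.5 | 0.08 to 0.35 | 6% to 33% |
| 0.5 | 0.5 | 0 | 5% |

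**Drift the other way.** Section I.2 puts BV recurrence at 30% within three months of treatment. At a constant rate this is 1 − 0.70^(1/3) = 11% by one month and 1 − 0.70^(2/3) = 21% by two months. The same rate gives 1 − 0.70² = 51% at six months, in line with the 50% in that section. If all 20 women had just been treated, that is about 2 and 4 relapses (20 × 0.112 = 2.2; 20 × 0.212 = 4.2) with no gel effect.

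**The case against.** The strongest case on the other side has four parts.

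*The study is modest in scale.* Its title calls it exploratory, it is sized and described as a pilot, and it states no rule for concluding causation. That is fair and limits the severity. Being a pilot does not, however, qualify the aims or the hypothesis, which remain causal as written.

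*Improvement by regression to the mean is not assured.* A reader might infer that women are picked at symptomatic visits and that improvement will therefore appear from regression alone. The Protocol does not support this. Eligibility rests on one-year history, recruitment is from scheduled appointments of unstated purpose or by poster, and symptoms at entry are permitted but not required. The home baseline and the 10-day waits loosen the link to any selecting episode. This objection stands, with one limit: the treatment-related wait covers only women on an acute course, so an untreated symptomatic woman can still give her baseline near a peak.

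*The direction is not shown for both outcomes.* Women are selected on symptoms and history, not on lactobacillus share, so nothing fixes the sign for the microbiome. This stands.

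*The unstated role of collection 3 is no fault.* Survey B and swabs are scheduled at all three points, and the choice of contrasts is commonly left to the SAP. This also stands.

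**Conclusion.** The point holds as a mismatch between aim and design: the trial can estimate within-woman change but cannot attribute it to Phexxi, and the planned regression does not repair this. That conclusion needs no numerical assumption.

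The size of the possible error is unknown. The range of 13% to 56% is an illustration for the symptom score and rests wholly on the assumed elevation and correlation. The excess disappears if baseline is no closer to the selecting episode than follow-up is. For the microbiome outcome, and for women treated shortly before baseline, even the direction is unknown.

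A reader might also infer that comparing collection 2 with collection 3 would serve as a causal check, since a change that recedes after stopping looks like a gel effect. It would not serve. Natural relapse would also produce a recession. For symptoms, the end of gel irritation would move the score the other way: Appendix F lists burning (18.0%), pruritus (14.5%) and discharge (5.5%), which overlap the Appendix C items. Persistence would be compatible with the hypothesised colonisation and with natural course alike.

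**What to change.** Reword the two primary aims and the hypothesis in Section I.1, the efficacy statement in Section I.3 and the planned conclusion as within-woman change from baseline during and after use of Phexxi. State that causation and efficacy are not tested, and that natural course, regression to the mean, recent treatment and relapse cannot be separated from a gel effect. In Section III.2, add that the regression describes variation between women and does not adjust for time or natural course.

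The change from collection 2 to collection 3 may be reported descriptively from data already collected, but not as a test separating gel effect from natural course.

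This is a change of wording only, with no added visits, patients or assays. The downside is a weaker claim. If a causal aim is to be kept, a concurrent control group would be needed; a second pre-treatment measurement would help to gauge regression to the mean but would not replace a control. Either is a larger change than this pilot requires.

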The presence of lactic acid-forming lactobacilli has been shown to promote eubiosis of the vaginal microbiome through several mechanisms, including the production of antimicrobial compounds (eg H₂O₂, lactic acid, bacteriocin-like substances), competition for adhesion sites in the vagina, as well as the formation of antibiotic-like compounds⁶. In a landmark trial done by Ravel et al. in 2010, four CST (community state types) were used to classify the vaginal microbiome of the study population. Of the four CSTs, CST 4, which contained primarily non-lactobacilli species, was most closely associated with the development of symptomatic BV or yeast infections. This community state type can be differentiated into three subtypes, all typified by higher proportions of anaerobic, non lactic-acid producing bacteria. Without a significant presence of lactic acid, the vaginal microbiome in this CST is vulnerable to disruption, which may be a possible contributing factor to the increased incidence of BV/yeast seen in this population⁷. We propose that by increasing the presence of lactic acid in the vaginal microbiome, there will be increased growth of lactic-acid forming bacteria, thereby decreasing the incidence of recurrent BV and yeast infections. In order to investigate this, we hope to study the effects of the lactic-acid containing vaginal gel, Phexxi, on the composition of the vaginal microbiome. Based on a review of the available literature, we will have participants insert the Phexxi insert and gel two times per week for 4 weeks.¹⁰

Phexxi is an intravaginal therapy containing lactic acid, citric acid, and potassium bitartrate. It is FDA-approved as a contraceptive agent, but is currently in product-funded studies for use as treatment for bacterial vaginosis, as well as a preventative agent for gonococcal and chlamydial infections.

3. Preliminary studies:

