Once received at the research site, samples will be stored in a specimen freezer at -80 degrees F until all specimens are received, at which point they will analyzed using NextGen sequencing, a DNA sequencing technology that will identify the genetic makeup of their specimens. This will be done to sequence the genome of the bacteria of the microbiome, not the patient's genetic material. The first phase of the study will also include a survey (Appendix B), which will collect demographic information from each participant, as well as assess patients' current acceptability of a vaginal gel for prophylactic use, their most bothersome symptoms, and how their quality of life is affected by recurrent vulvovaginitis. The specific information collected from each

participant can be found below in Data Analysis. The survey used to measure this will be the **Vulvovaginal Symptom Questionnaire (VSQ)**, which has been validated for the purposes stated above (Appendix C). There will also be an added space in the survey provided for open-ended answers and comments.

Measurement for primary outcomes will be done using two separate methods. In order to assess for the presence of lactic acid-forming organisms before and after the lactic acid gel intervention, NextGen DNA sequencing will be completed on self-collected samples submitted by participants. The analysis of these samples will be performed by [name], at an in-house lab run by the UH Maternal Fetal Medicine division. In order to assess for patient-experienced symptoms, **survey B (Appendix C) will be administered prior to, immediately after, and 30 days after intervention.**

In order to measure our secondary outcome, Survey C (Appendix D) will be administered at collection points 2 and 3.

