Appendix B Patient demographic survey

Demographic Survey

Subject ID:

1: What is your age?:

2: What is your race?

3. Are you Hispanic/Latinx?

4.: How many yeast infections or episodes of bacterial vaginosis (BV) have you had in the last year?

5: Are you on any kind of birth control? If yes, what kind?

6: In the next portion, please describe what kinds of food you normally eat in a typical day. In addition to meals, please include snacks. If you are currently on a specific type of diet, please state that here.

Breakfast

Lunch

Dinner

Other

7 What other medical conditions have you been diagnosed with? If none, please write, "none".

8: Please list any medications/supplements you are currently taking. If none, please write, "none".

Appendix C. Survey to assess vulvovaginitis symptoms. Modified version of the Vulvovaginitis Symptom Questionnaire (VSQ)

During the past week, have you been bothered by:

1. Your vulva itching? 0 No 1 Yes

2. Your vulva burning or stinging? 0 No 1 Yes

3. Your vulva hurting? 0 No 1 Yes

4. Your vulva being irritated? 0 No 1 Yes

5. Your vulva being dry? 0 No 1 Yes

6. Discharge from your vulva or vagina? 0 No 1 Yes

7. Odor from your vulva or vagina? 0 No 1 Yes

8. Worry about your vulvar symptoms? (for example, that it will spread, get worse, scar, etc.) 0 No 1 Yes

9. The appearance of your vulva? 0 No 1 Yes

10. Frustration about your vulvar symptoms? 0 No 1 Yes

11. Embarrassment about your vulvar symptoms? 0 No 1 Yes

- 12. The effects of your vulvar symptoms on your interactions with others? 0 No 1 Yes
- 13. The effects of your vulvar symptoms on your desire to be with people? 0 No 1 Yes
- 14. Your vulvar symptoms making it hard to show affection? 0 No 1 Yes
- 15. The effects of your vulvar symptoms on your daily activities? 0 No 1 Yes
- 16. Your vulvar symptoms affecting your desire to be intimate? 0 No 1 Yes
- 17. Are you currently sexually active with a partner?
 No → Thank you. You are done with this questionnaire. Yes → Please proceed with the next 4 questions
- 18. The effects of your vulvar symptoms on your sexual relationships? 0 No 1 Yes
- 19. Your vulvar symptoms causing pain during sexual activity? 0 No 1 Yes
- 20. Your vulvar symptoms causing dryness during sexual activity? 0 No 1 Yes
- 21. Your vulvar symptoms causing bleeding during sexual activity? 0 No 1 Yes

Please use the space below to list any vulvar/vaginal symptoms you are experiencing which have not already been listed.

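### Section I.3 states an aim of prophylactic efficacy, but no follow-up form asks about a new BV or yeast episode or its treatment, so a relapse treated after the gel course can pass as improvement

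*Protocol*

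**What the plan says.** **The aim.** Section I.3 (Preliminary studies) closes its argument with: "This study aims to explore the feasibility and efficacy of a lactic acid-containing gel as prophylaxis against recurrent BV/yeast infections". Section I.2 expects more lactic acid-forming bacteria, "thereby decreasing the incidence of recurrent BV and yeast infections".

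**The outcomes.** Section I.1 lists two primary outcomes: "To assess if the use of Phexxi causes changes in the vaginal microbiome" and "To assess if the use of Phexxi decreases vulvovaginitis symptoms in study participants". The secondary outcome is satisfaction and acceptability. Section III.1 restates the primaries: "The primary outcomes will be an increase in lactic acid-forming lactobacilli, as well as a decrease in patient-reported symptoms of vulvovaginitis". Recurrence appears in neither list.

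**The forms.**
- Appendix B, the demographic survey of the first phase, asks "How many yeast infections or episodes of bacterial vaginosis (BV) have you had in the last year". No repeat is planned.
- Survey B (Appendix C) is a yes/no symptom list that opens "During the past week, have you been bothered by". It "will be administered prior to, immediately after, and 30 days after intervention". Its free-text box is for symptoms not already listed.
- Survey C (Appendix D) covers acceptability, appropriateness and feasibility at collections 2 and 3.
- The diary (Appendix E, described in Section III.1) belongs to the 30 treatment days. It has free-text columns for symptoms or side effects and for other events, with new medication as one example.

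**Interim treatment.** The note in Section II.2 and Section III.1 ask for a 10-day wait after antibiotic or antifungal treatment before the baseline swab. Nothing comparable is recorded for collections 2 and 3.

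**The concern.** An aim of prophylactic efficacy needs a record of whether the infection came back. The follow-up forms ask how a woman felt in the last seven days and what she thinks of the product. They do not ask whether she had BV or a yeast infection since the last swab, or whether she took anything for it.

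The gap also reaches the listed primary outcomes at collection 3:
- **Symptoms.** A woman who relapses after the gel course and is treated successfully before the last recall week can report no symptoms and score as improved. The improvement would belong to the antibiotic or antifungal.
- **Microbiome.** The protocol accepts that such treatment disturbs the flora, since it imposes a wait before baseline. The third swab is exposed to the same disturbance, with no item to show which swabs are affected.

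A statistical analysis plan can decide how to handle these women, but it cannot identify them if the information was never collected.

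**Working it through.** **Sample size, for reference.** Section II.1 gives 20 from a 95% confidence level and a 15% prevalence. The problem-detection formula gives ln(1 − 0.95)/ln(1 − 0.15) = 18.4, so 19, which is close to the stated 20. Adding 10% gives 20 × 1.10 = 22, as enrolled. The point does not rest on this figure; 20 is used below as the number of women with data.

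**Days with no instrument.** Follow-up is 30 treatment days plus 30 days to collection 3, about 60 days.
- Diary, if kept daily: 30 days.
- Survey B at collection 2: 7 days, inside the diary period.
- Survey B at collection 3: 7 days.
- Uncovered: 60 − 30 − 7 = 23 days, and 23/60 = 38%.

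**How many episodes might occur.** Section I.2 gives BV recurrence of 30% within three months and 50% within six months of treatment. Assume a constant hazard, the BV rate for all women, and a clock that starts with the study.
- From the three-month figure: 1 − 0.7^(60/90) = 0.212, and × 20 = 4.2 women.
- From the six-month figure: 1 − 0.5^(60/180) = 0.206, and × 20 = 4.1 women.

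**How many would start in the 23-day gap** (days 30 to 53), on the same assumptions:
- Three-month figure: 0.7^(30/90) − 0.7^(53/90) = 0.888 − 0.811 = 0.077, and × 20 = 1.5 women.
- Six-month figure: 0.5^(30/180) − 0.5^(53/180) = 0.891 − 0.815 = 0.076, and × 20 = 1.5 women.

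**What recording episodes would yield.** The exact (Clopper-Pearson) 95% interval for 4/20 is 5.7% to 43.7%. Against a fixed rate of 21%, a one-sided 5% exact test rejects only with no events at all: 0.79^20 = 0.009, whereas one event or fewer has probability 0.009 + 20 × 0.21 × 0.79^19 = 0.057. Power for a halved rate is 0.895^20 = 0.11. The result can only be descriptive.

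**The case against.** **Prophylaxis is not the study's formal aim.** Section I.1 names microbiome, symptoms and acceptability, and each has an instrument. A reader might infer from Section I.3 that the trial lacks its main endpoint. The documents do not support that: the sentence sits under Preliminary studies and speaks of exploring, and Survey C partly serves its feasibility half. What stands is a mismatch between Section I.3 and the outcome lists.

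**Some episodes may still be noted.** The diary has dated rows with room for symptoms and new medication. Appendix F lists vulvovaginal mycotic infection (9.1%) and BV (8.4%) as adverse reactions, and Section IV.3 withdraws women who develop side effects. An episode during treatment could therefore be noted, or could take the woman out of the study, and she would not then be silently counted as improved. This stands, but it is incidental, undefined free text, and withdrawal would lose the later data of women who recur.

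**Counting only Survey B exaggerates the gap.** A reader might infer that 46 of 60 days (77%) are unobserved, because two one-week recalls cover 14. That ignores the diary; 38% is the fairer figure if the diary is kept daily. Coverage is less certain than that, because Section III.1 ties entries to product use. Appendix E also asks for the diary with the second specimen but dates this 30 days after the drug is completed, whereas Section III.1 puts collection 2 at the end of the intervention. Those passages must be reconciled.

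**Extra questions would not prove prevention.** This stands in full. Women serve as their own controls, may enter with symptoms, and are selected for two or more episodes in the past year, so a later fall could be regression to the mean.

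**Conclusion.** The point holds as a mismatch between one stated aim and the data collected, together with a missing data item that affects the primary symptom and microbiome comparisons at collection 3. It is worth fixing because the fix is cheap and the information is hard to recover reliably later.

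The gap is about 23 of 60 days (38%), assuming a diary kept daily through treatment. The expected count of about 4 of 20 women in 60 days, with about 1.5 starting in the gap, is illustrative only: it applies a BV rate measured from treatment to a mixed BV and candida group at unknown times since treatment, and the documents give no yeast recurrence rate. Not every such woman would be treated and symptom-free by the last recall week, so 1.5 is closer to a ceiling than to a count of women wrongly scored as improved.

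A reader might also infer that a recurrence item would let the trial test prophylaxis. It would not, in an uncontrolled pre-post pilot of this size.

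**What to change.** 1. Add two questions to Survey B at collections 2 and 3: whether the woman has had BV or a yeast infection since her last swab (which, when, diagnosed or self-diagnosed), and whether she took any antibiotic or antifungal in that time.
2. Report the proportion with an episode and its exact 95% CI, labelled exploratory.
3. Flag women treated between collections in the symptom and microbiome comparisons, and give a sensitivity analysis for them. The detail can go in the analysis plan.
4. Reword the Section I.3 aim so that it matches the listed outcomes and claims no evidence of preventive efficacy.
5. Reconcile the diary's return instruction in Appendix E with Section III.1.

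The cost is two questions on a survey already being sent, one descriptive table and a few lines of protocol text. The downside is few events and a wide interval. Step 4 alone would repair the mismatch in the aim, but would leave the collection 3 comparisons exposed to unrecorded treatment.
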